7.2.1. Verify eligibility (see section 0)

7.2.2. Make sure that the information needed for registration is available:

- E2 level used to determine premenopausal status
- Type of surgery intended to be performed upon completion of neoadjuvant treatment
- Patient age in years
- Prior fertility treatment yes/no, date of last such treatment
- Date of most recent pregnancy test

7.2.3. Obtain written Informed Consent both for the clinical trial and biological material submission, signed and dated by the patient and Investigator. Informed consent must be obtained prior to any trial-specific screening procedure or intervention.

7.2.4. Directly access the IBCSG Registration/Randomization System and provide the requested information as indicated on the Confirmation of Registration (41-A) Form. The date the Informed Consent Form and the Biological Material Consent was signed by the patient and the date signed by the Investigator are both required to complete randomization.

The IBCSG Registration/Randomization System will provide the following information via e-mail:

- Patient ID (randomization number)
- Treatment assignment
- Date of randomization

- 7.2.5. Submit the Confirmation of Registration (41-A) electronic case report form (eCRF) via iDataFax. The patient binder of eCRFs will be available in iDataFax within 24 hours of successful randomization.

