15.2. Secondary objectives

Secondary objectives include evaluation with respect to several secondary endpoints as defined in section 4.2. Analyses of the secondary endpoints will be descriptive. Tests of significance, whenever applicable, will not be controlled for multiple comparisons. Due to the limited sample size, the tests will largely be underpowered except in cases where differences between treatment groups are substantial. Randomized patients who received at least one dose of study treatment are included in the analysis unless otherwise indicated.

15.2.1. Tolerability (Safety of combined neoadjuvant therapy):

Tolerability will be evaluated in each treatment arm separately. Randomized patients who received at least one dose of the trial treatment will be included in the tolerability analyses.

The frequencies of adverse events (AE) according to CTCAE 4 by type and worst grade experienced while on the neoadjuvant treatments will be summarized and tabulated by treatment arms. Two-sided 90% confidence interval (CI) for the difference in proportion of patients with each type of grade 3 or higher targeted adverse event (see section 13.2) between the treatment arms will be assessed.

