15.2.6. Breast-conserving surgery (BCS) rate

The proportion of patients undergoing BCS is evaluated in two analyses. First, considering all patients enrolled, the percent of patients in each treatment arm who had a breast-

conserving surgery will be presented, and the difference between the treatment arms assessed using a two-sided 90%CI. Second (i.e., rate of conversion), considering only patients who are reported at baseline not to be candidates for BCS, the percent in each treatment arm who had a BCS after neoadjuvant therapy will be presented, and the difference between the arms assessed using a two-sided 90% CI.

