2.2.6 Analyses of secondary endpoints

- Node negative disease at surgery: The percentage of patients with node-negative disease at surgery will be descriptively summarized by treatment arm. Two sided 90% CI for the difference in percentage of patients with node-negative disease between treatment arms will be reported.
- Breast-conserving surgery (BCS):
 - Details of the surgical procedure performed overall and according to treatment arms.
 - The percent of patients in each treatment arm who had a breast-conserving surgery were presented, and the difference between the treatment arms were assessed using a two-sided exact 90% CI.
 - Rate of conversion (patient identified as candidates/planned for BCS or mastectomy per data on RA-form vs surgery performed on C-form): Cross-tabulation of surgery status between “planned” vs ‘performed’ and the percent in conversion overall and according to treatment arms were presented.
- Change in Ki67 (Surgery population, unless otherwise noted)
 - Ki67 expressions at baseline (pre-treatment, based on ITT population) and at surgery were descriptively summarized (median, IQR and mean) according to treatment arms.
 - The change in Ki67 expression from baseline (pre-treatment) to surgery was summarized for each treatment arm and two-sided 90% CI for the change were calculated and explored using a paired sample Wilcoxon signed-rank test.

- The percentage changes in Ki67 expression between the treatment arms from baseline to surgery were assessed using a two-sided 90% CI and explored using a two-sample Wilcoxon rank sum test.
- Boxplots were used to illustrate the marker distribution at baseline and surgery timepoints.
- Spider plots were used to show the individual paired Ki67 data from baseline to surgery.
- The preoperative endocrine prognostic index (PEPI) score at time of surgery
Patients in surgery population will be included in the assessment. Descriptive statistics are used to summarize the PEPI score by treatment arm. Two-sided 90% CI for the difference in the PEPI scores between the two arms maybe constructed. (*NOT DONE, given only one pt had PEPI score of 0*)
- Objective response was defined as CR/PR vs. Others (SD/PD/NE), where NE stands for non-evaluable:
 - Best overall response, overall and by treatment arm, were provided with Ns and proportions.

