3.8 BREAST CONSERVAING SURGERY (BCS) RATE

- Table of surgery received by treatment arms, difference in BCS rate between arms, 90%CI.
- Table of BCS conversion from planned or (candidate) at baseline to actual received

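### The between-arm BCS difference ignores the surgery intended at registration, which gives up precision that data already collected could recover

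*SAP*

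**What the plan says.** For the arm comparison of BCS, SAP 2.2.6 presents the percentage in each arm and states that "the difference between the treatment arms were assessed using a two-sided exact 90% CI". SAP 3.8 lists the matching output: "Table of surgery received by treatment arms, difference in BCS rate between arms, 90%CI". Neither names a covariate or stratum. SAP 2.2.4 limits the analysis to patients who had surgery.

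Protocol 7.2.2 lists, among the items needed to register a patient, "Type of surgery intended to be performed upon completion of neoadjuvant treatment". It is therefore known before randomization. Protocol 7.5 stratifies randomization by age only, with dynamic balancing by institution.

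The SAP uses intended surgery in one place, a cross-tabulation of planned against performed operations, where "the percent in conversion overall and according to treatment arms were presented". No between-arm interval is stated for conversion. Protocol 15.2.6 has two BCS analyses. The first covers all enrolled patients, "and the difference between the treatment arms assessed using a two-sided 90%CI". The second is the conversion rate, "considering only patients who are reported at baseline not to be candidates for BCS", also with a 90% CI for the arm difference.

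**The concern.** Protocol 3.1 describes tumor shrinkage that permits conservation as the one demonstrated benefit of primary systemic therapy, so readers will look at the BCS comparison. If patients already planned for conservation mostly receive it, and those planned for mastectomy mostly do not, a crude difference pools two groups with very different rates. The between-group variation then widens the interval, although a baseline variable that could remove it is on file. The plan adjusts elsewhere: the primary test is stratified by age, with a covariate-adjusted Cox model (SAP 2.2.5), and the symptom model controls for age (SAP 2.2.6). At stake is the width of the only interval that the SAP states for a BCS arm difference.

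**Working it through.** **Inputs from the documents.** 25 patients per arm (Protocol 5.2; 51 were finally enrolled, SAP 1.4.1), two-sided 90% interval. The size of the surgery population is not given, so 25 is the planned number. The plan states no BCS rate, precision or power, so it has no figure of its own to reproduce.

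**Assumptions.** Let s be the share intended for BCS, and pB and pM the BCS rates in intended-BCS and intended-mastectomy patients. The documents give none of these. I take s = 0.5 and a range of (pB, pM).

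**Formulas.**
- Overall rate: p = s·pB + (1−s)·pM
- Crude SE = √[2p(1−p)/25]
- Stratified SE = √{2[s·pB(1−pB) + (1−s)·pM(1−pM)]/25}
- Half-width = 1.645 × SE
- Share of variance due to intended surgery = s(1−s)(pB−pM)² / [p(1−p)]

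**Worked case, 85%/20%.** p = 0.525. Crude SE = √(2 × 0.2494/25) = 0.141, half-width 0.232. Stratified SE = √(2 × 0.14375/25) = 0.107, half-width 0.176.

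| pB / pM | Crude half-width | Stratified half-width | Narrower by | Variance share |
|---|---|---|---|---|
| 60% / 40% | 0.233 | 0.228 | 2% | 4% |
| 80% / 30% | 0.231 | 0.200 | 14% | 25% |
| 85% / 20% | 0.232 | 0.176 | 24% | 42% |
| 90% / 10% | 0.233 | 0.140 | 40% | 64% |

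**Simulation at 25 per arm, s = 0.5.** The crude half-width was about 0.228. Stratified half-widths were 0.220-0.225 (60%/40%), 0.192-0.197 (80%/30%) and 0.173 (85%/20%), slightly below the formula values. With s from 0.3 to 0.7, the variance reduction was 3-4% at 60%/40%, 21-25% at 80%/30% and 43-50% at 90%/20%.

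**Chance imbalance.** The SD of the arm difference in the intended-BCS share is √(2 × 0.25/25) = 0.141. Multiplied by (pB−pM), a 1-SD imbalance moves the crude difference by 7 points at 80%/30%, 9 at 85%/20% and 11 at 90%/10%. An imbalance of 20 points or more has a probability of about 16% (s = 0.3 or 0.7) to 20% (s = 0.5). This movement is already inside the crude SE: at 85%/20%, 0.0919² + 0.1072² = 0.00845 + 0.01150 = 0.01995, which is exactly the crude variance. In simulation with no treatment effect, the crude estimate averaged 0.00 and its nominal 90% Wald interval covered 88-89%.

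**Does stratifying break the interval?** With s = 0.5 and no effect, the stratified interval excluded zero in 10.8% to 12.6% of runs across 60%/40%, 80%/30%, 90%/20% and 95%/10%. Coverage is therefore about 87-89%, similar to crude Wald. The exact crude interval for 12/25 against 12/25 runs from −0.24 to 0.24, about a point wider each side than Wald.

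**What the precision buys, one illustration.** Take s = 0.3, rates 90%/20%, and a 30-point gain confined to intended-mastectomy patients, so the true difference is 0.7 × 0.30 = 0.21. The chance that the 90% interval excludes zero rises from 48% crude to 58% stratified.

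**The case against.** The strongest reply is that nothing is wrong with a crude difference and an exact interval here. The protocol says "Analyses of the secondary endpoints will be descriptive" and concedes that "the tests will largely be underpowered except in cases where differences between treatment groups are substantial". No decision rests on BCS, and about 25 patients per arm remains the main limit: at 85%/20% the half-width is still 17-18 points after stratifying. The size of the gain rests on rates that the documents do not give, and at 60%/40% it is negligible. All of this stands. It makes the point one of efficiency, not error. But a descriptive endpoint is read through its interval, and the weak-association case costs almost nothing.

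A second reply is that intended surgery is already handled. The protocol's non-candidate comparison does condition on it. The SAP, however, reports conversion percentages without an arm-difference interval, so its only stated BCS interval ignores the variable.

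A third is that strata of about 12 per arm are too small for an asymptotic interval. The simulated coverage does not bear this out: even at 95%/10% it was about 89%.

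A fourth is that the SAP already records results in places (for example, that only one patient had a PEPI score of 0), so a covariate added now is chosen late. That stands, and it calls for labelling.

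A reader might also infer that intended surgery is the strongest predictor of the operation performed, and that imbalance in it dominates or biases the crude comparison. The documents do not support this. They report no such association. Randomization keeps the crude estimate unbiased, and its interval already carries the imbalance. In three of the four cases tabulated, most of the variance lies within strata.

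**Conclusion.** The point holds as a loss of precision on a descriptive secondary endpoint. The planned interval is valid but wider than it need be if intended surgery predicts performed surgery. With 25 per arm and half intended for BCS, stratifying takes the 90% half-width from about 23 points to between 22-23 (weak association, 60%/40%) and 14 (very strong, 90%/10%). Intermediate values are about 20 at 80%/30% and 17-18 at 85%/20%. Every rate and the intended-BCS share are assumptions. The conclusion that adjustment is feasible and nearly free does not depend on them; the size of the gain does.

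**What to change.** Add to SAP 2.2.6 and 3.8 a between-arm risk difference in BCS stratified by surgery intended at registration (BCS or mastectomy), by Mantel-Haenszel or stratified Miettinen-Nurminen, with a two-sided 90% CI. Label it as an added analysis, and keep the crude difference with its exact interval alongside. The cost is one further analysis line on data already held. The small downside is that the stratified interval is asymptotic, with simulated coverage of about 88%, similar to crude Wald, whereas the planned crude interval is exact.

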7.5. Stratification

For randomization, patients will be stratified by age (in years): less than or equal to 39 vs 40 or more.

Dynamic institution balancing will be used in order to balance randomized assignments within institutions.

8. Study drugs formulation and handling

Triptorelin, degarelix and letrozole are the investigational drugs used in this trial; all will be supplied.

Complete details of the study drug logistics, distribution, packaging, labeling and handling are described in a separate drug supply manual.

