15.2.2. Changes in Ki67 expression levels

Patients who received at least one dose of study treatment and who have biospecimen available will be included in the analysis.

- The percentage change in Ki67 expression (geometric means*) from pre-treatment to surgery will be summarized for each treatment arm and two-sided 90% CI for the change will be calculated.
- The percentage changes in Ki67 expression (geometric means*) between the treatment arms at baseline and surgery are assessed using a two-sided 90% CI and explored using a two-sample Wilcoxon Rank Sum test.
- Other descriptive summary such as boxplots for the marker data will be provided.

** Due to the approximate lognormal distribution of the data*

In cases with no residual invasive tumor detected at surgery, the percentage change in Ki67 will be recorded as 100%.

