2.2.4 Secondary Endpoints

1. Node-negative disease at surgery: The number of lymph nodes assessed at surgery minus the number of positive nodes identified, equal to zero.
2. Breast-conserving surgery (BCS): Whether or not patient undergoes BCS (per Surgery form). If patient does not undergo surgery within the trial then patient is to be excluded from the surgery outcome summary (analysis is based on surgery population)
3. Change in Ki67 expression level: the percent change in Ki67 expression from pre-treatment diagnostic (baseline) biopsy to surgery, calculated as (surgery-baseline)/baseline*100.
4. The Preoperative Endocrine Prognostic Index (PEPI, range 0-12) score at time of surgery: By integrating central pathology review (CPR) results of pathological features and biomarkers with risk points (table below), the PEPI is the sum of the risk points with a 0 score representing the best prognostic feature, as previously determined to be associated with recurrence-free survival (RFS):

Pathology, biomarker status	RFS	
	HR	Adverse Points
Tumor size:		
T1/2		0
T3/4	2.8	3
Nodal status		
Negative		0
Positive	3.2	3
Ki67 level		
0 – 2.7% (0 – 1 ^a)		0
>2.7 – 7.3% (1 – 2 ^a)	1.3	1

>7.3 – 19.7%	(2 – 3 ^a)	1.7	1
>19.7 – 53.1%	(3 – 4 ^a)	2.2	2
>53.1%	(>4 ^a)	2.9	3
ER status, Allred score			
0 – 2		2.8	3
3 – 8			0

^aThe natural logarithm interval corresponding to the per cent Ki67 values on the original percentage scale

5. Best overall response: based on WHO tumor measurement and response criteria [1], measured from the start of treatment across all time points until disease progression or the end of 6 cycles of neoadjuvant therapies, whichever comes first. Response was determined by the IBCSG Head of Medical Affairs. An internal review (IR) form was created to record the final determination on best overall response. Confirmation of partial or complete response by an additional scan was not required in this trial.

Best overall response was assessed based on changes in tumor size from baseline to the assessments after 3 and after 6 cycles (denoted as day 1 of cycle 4 and prior to surgery respectively) as measured physically by caliper or ruler and as measured by breast tumor imaging (i.e., bilateral mammography and breast ultrasound).

- Complete Response (CR): The disappearance of all known disease;

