3.4 PATIENT DEMOGRAPHICS AND BASELINE DISEASE AND PRIOR TREATMENT

Characteristics of the ITT population will be summarized overall and according to treatment assignment. Continuous variables are summarized descriptively (e.g., mean, SD, minimum, maximum, and interquartiles(IQR)). Categorical variables are summarized as N (%); for variables with unavailable (missing, unknown, not done) values, the default approach is to list the number of unknowns as a category but calculate percentages excluding these unknowns from the denominator.

- Stratification factors (as analyzed)
- Patient:
 - Age at randomization
 - BMI at randomization
 - ECOG Performance status at randomization
 - Smoking status/history
 - Oral contraceptive use
 - Centrally assessed baseline E2 levels)
 - Baseline AE/symptoms, comorbidity history
- Pre-treatment Disease characteristics:
 - Tumor size or tumor lesion (via WHO criteria): product of maximum diameter (MD) and largest perpendicular diameter (LPD) of target lesions at baseline), multiple assessments (clinical, mammography, ultrasound)
 - Grade (centrally assess via core biopsy)
 - Histologic type (ductal, lobular, not determinable)
 - ER, PgR status, Allred score, and Her2 status of core biopsy
 - Clinical Nodal status
 - Ki67 label index (%)
 - Baseline CEA, CA15-3: CEA (carcinoembryonic antigen) and CA15-3 (breast cancer associated antigen)
- Prior Treatment (Hform):
 - Type of prior endocrine therapies: SERM, AI and GnRH/LHRH agonist (eligibility exclusions for any endocrine Rx taken within 12 months or oral contraceptive use within 2 months of rando), mainly to confirm not taken it.
- Tables
 - Characteristics, overall ITT population and by treatment assignment

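### The between-arm Ki67 comparison fixes the baseline slope instead of estimating it and leaves out the age stratum: valid, but possibly less precise than it could be

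*SAP*

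**What the plan says.** SAP 2.2.4 (item 3) defines the Ki67 endpoint as percent change from the diagnostic biopsy to surgery, "calculated as (surgery-baseline)/baseline*100". For the arm comparison SAP 2.2.6 says: "The percentage changes in Ki67 expression between the treatment arms from baseline to surgery were assessed using a two-sided 90% CI", and the difference is also "explored using a two-sample Wilcoxon rank sum test". No covariate or stratum is named.

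Protocol 15.2.2 has the same structure (90% CI, and "explored using a two-sample Wilcoxon Rank Sum test") but works with geometric means, "Due to the approximate lognormal distribution of the data". It adds a rule for patients with no residual invasive tumour at surgery: "the percentage change in Ki67 will be recorded as 100" percent. The SAP does not repeat that rule.

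Both candidate covariates are available. SAP 3.4 lists "Ki67 label index" among the pre-treatment characteristics, and Protocol 7.5 says: "For randomization, patients will be stratified by age (in years): less than or equal to 39 vs 40 or more". Other analyses in the plan do adjust. The primary log-rank test is stratified by age (Protocol 15.1.2, SAP 2.2.5), the supportive Cox model includes baseline E2 (same sections), and the patient-reported symptom model controls for age (Protocol 16.6.1, SAP 2.2.6).

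Protocol 15.2 calls the secondary analyses descriptive, without multiplicity control and largely underpowered.

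**The concern.** Dividing by baseline does not in general make the result independent of baseline. On the log scale, percent change corresponds to log surgery value minus log baseline value, that is, a regression on baseline with the slope set to 1. If the true slope differs from 1, two things follow. The change score carries baseline variation that a fitted slope would remove, so the CI is wider than it need be. And a chance difference in baseline Ki67 between arms passes in part into the estimated treatment difference.

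Nothing in the design balances baseline Ki67: randomisation is stratified by age with institution balancing only. A between-arm CI is what the plan promises for this endpoint, so its width is what is at stake, in a trial that already expects limited power here.

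**Working it through.** **Plan's own figure.** There is none for Ki67: no SD, correlation, effect size or power. The stated 90% power with 23 per arm concerns the primary log-rank test and does not bear on this point. All Ki67 inputs below are therefore assumptions.

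**Formulas.** Let s0 and s1 be the SDs of log Ki67 at baseline and surgery, and rho their correlation. Per patient, the variance relevant to the arm difference is:

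- log change: s0² + s1² − 2·rho·s0·s1
- baseline-adjusted model (large sample): s1²·(1 − rho²)

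The ratio of CI widths is the square root of the second over the first. With equal SDs it is sqrt((1 + rho)/2). The fitted slope is rho·s1/s0, and there is no gain when it equals 1.

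**Worked cases.**

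- Equal SDs, rho 0.2: sqrt(0.6) = 0.775, so 23% narrower. At rho 0.6: sqrt(0.8) = 0.894, so 11% narrower. The matching variance ratios, 2/(1 + rho), are 1.67 and 1.25.
- SDs 0.6/1.0, rho 0.2: change 0.36 + 1.00 − 0.24 = 1.12, adjusted 0.96, sqrt(0.96/1.12) = 0.926, so 7% narrower. At rho 0.6 both variances are 0.64 and the slope is 0.6·1.0/0.6 = 1, so there is no gain.
- SDs 1.0/0.6, rho 0.4: change 0.88, adjusted 0.36·0.84 = 0.302, sqrt(0.302/0.88) = 0.586, so 41% narrower.

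Reduction in CI width against log change:

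| Log SD baseline / surgery | rho 0.2 | rho 0.4 | rho 0.6 |
|---|---|---|---|
| equal | 23% | 16% | 11% |
| 0.7 / 0.9 | 14% | 8% | 2% |
| 0.6 / 1.0 | 7% | 2% | 0% |
| 1.0 / 0.6 | 44% | 41% | 40% |

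**Simulation at trial size.** With 25 per arm, assumed medians of 20% and 4%, and 1,500 runs per setting, the reductions were 22%, 16% and 11% for equal SDs and about 6%, 1% and 0% for 0.6/1.0. The chance that the 90% CI excludes no difference, at a true log difference of −0.6, was:

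| SDs, rho | raw percent change | log change | adjusted |
|---|---|---|---|
| 0.8/0.8, 0.4 | 0.65 | 0.77 | 0.87 |
| 0.6/1.0, 0.6 | 0.73 | 0.84 | 0.83 |

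Part of the distance between the SAP's raw percent change and the adjusted model is therefore a scale effect and not an adjustment effect.

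**Chance imbalance.** At 25 per arm, one standard error of the baseline difference is sqrt(2/25) = 0.28 SD. With no treatment effect and SDs of 0.8, the log-change difference shifts by (slope − 1)·0.28·0.8. At rho 0.2 that is −0.8·0.224 = −0.18. Across rho 0.2 to 0.8 the simulated shift in the percent-change difference was 5.9 down to 1.0 points in size, while the adjusted estimate stayed near zero.

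**Age.** If the stratum explained 0 to 10% of residual variance (assumed), the CI would narrow by 0 to 1 − sqrt(0.9) = 5%.

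**Zeros.** Suppose a zero at surgery is replaced by a constant c on the log scale, ignoring covariates. One such patient among 25 moves that arm's geometric mean by exp(ln(10)/25) − 1 = 10% between c = 0.1 and c = 1, and by exp(ln(100)/25) − 1 = 20% between 0.01 and 1. Two such patients give 20% and 45%.

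**The case against.** The case for leaving the plan alone has real content.

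- **Descriptive status.** This is one of seven unranked secondary endpoints, and the plan itself calls the comparison exploratory. That stands and limits the severity. It does not remove the point, since a between-arm CI is still promised.
- **Validity.** A reader might infer that the comparison is biased or invalid. The documents do not support that. Treatment is randomised, and simulated type I error for the unadjusted methods was 8% to 12% against a nominal 10%. Imbalance would also be visible, because baseline and surgery values are tabulated and plotted by arm.
- **Use of baseline.** A reader might infer that baseline Ki67 is ignored. It is not: it is the denominator. The Wilcoxon test on percent change ranks patients exactly as one on the log ratio would. The narrower point is that the slope is fixed at 1.
- **Cost of a log model.** It depends on how zeros are handled, whereas the rank test does not. This stands and has to be met in the fix.
- **Timing.** The SAP carries notes that reflect results: in 2.2.5 on suppression by the end of cycle 1, and in 2.2.6 on a single patient with a PEPI score of 0. PEPI is built partly from surgical Ki67, so Ki67 data may already have been seen. Replacing the planned comparison would then be post hoc. This also stands.

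**Conclusion.** The point holds as a minor one. Neither document estimates the baseline slope or uses the age stratum in the Ki67 arm comparison, although both variables are to hand and similar adjustments appear elsewhere in the plan.

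The size cannot be fixed from the documents. For rho between 0.2 and 0.6 it runs from no gain (slope near 1) through 11% to 23% (equal log SDs) to about 40% (baseline SD well above surgery SD). A reader might take 11% to 23% as the established loss. That needs equal SDs, which the documents do not give, and it is measured against log change and not against the SAP's raw percent change. The benefit of age is unknown and probably small. Nothing here touches the primary endpoint or its conclusion.

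**What to change.** Add a linear model of log Ki67 at surgery on arm, log baseline Ki67 and age stratum (≤39 vs 40+). Report the ratio of adjusted geometric means with its 90% CI. This agrees with the geometric-mean wording in Protocol 15.2.2.

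With it:

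- Keep the planned percent-change CI and Wilcoxon test. Label the model supplementary if Ki67 data had already been seen.
- State in advance how zero Ki67 and no residual tumour are handled, and show results for more than one offset.
- Reconcile the sign. The Protocol records no residual tumour as 100%, while the SAP formula with a surgery value of 0 gives (0 − baseline)/baseline·100 = −100%. Entered literally under the SAP formula, +100% would read as a doubling.

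The cost is SAP wording and one model, with no new data. The downsides are two degrees of freedom, which with a slope near 1 can leave the CI marginally wider (simulated standard error 0.228 against 0.226 for SDs 0.6/1.0 at rho 0.6), and some dependence on the offset.
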